Patients will be randomly assigned to either a control or experimental group allocated in the ratio of 1:1 by use of a computer-generated randomization schedule. Patients will be stratified according to whether they have undergone lumpectomy or mastectomy. We will randomize the block size to between 4 and 8 patients per block. Each block will therefore consist of patients who have undergone either lumpectomy or mastectomy, allocated in a 1:1 ratio. Block size will be concealed to the investigators until the end of the trial (i.e. after data analysis and statistical evaluation). The allocation sequence will be generated by a staff member with no other involvement in the trial. Assignments will be placed in sequentially numbered, opaque, sealed envelopes with the randomization number printed on them. These envelopes will be packed by a staff member with no other involvement in the trial. Every assignment will contain a code that corresponds to tubes of the melatonin/DMSO or placebo preparation. The primary investigator will enroll and assign participants to intervention on the basis of the assignment code from the envelope. Envelopes as well as tubes with active and placebo cream will be stored in a locked cabinet at Rigshospitalet.

Outcome assessment will be performed by the primary investigator, who is blinded to treatment allocation. Participants are also blinded to treatment allocation. The primary investigator will be blinded when performing data analysis and statistical evaluations.

Should the investigator deem it necessary for the safety of the patient, the investigator can un-blind a patient. Treatment-allocation will be noted in a document on a secure folder on a drive on the server of the Region Hovedstaden. Should an investigator need to un-blind a patient, they can access this document from their computer. Treatment allocation will only be un-blinded if it is imperative to the treatment of the patient. The treatment allocation will in this case only be

revealed to one other investigator than the primary investigator. This investigator will oversee the treatment of the patient. Registration of adverse reactions is described in the “Harms” section.

Drop-outs and patient retention

We plan to promote participant retention and complete follow up by asking for contact information (phone number and e-mail) and preferred way of contact. We will schedule appointments with patients at same location, accommodating their calendar, as far as possible.

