If a patient does not wish to complete all three follow-up visits, some of the outcomes can be filled in electronically from home, should the patients wish to do so. These outcomes are the QLQ-C30 and QLQ-BR23 questionnaires, and steroid usage outcomes. All data from drop-outs will be used in statistical analyses. Discontinuation of treatment will only occur in the following eventualities: the patient withdraws consent, or if the sponsor decides to terminate the study due to serious adverse events.

Conclusion of study

Recruitment of patients will be concluded when 48 patients have completed the study (see sample size calculations below, in the “Statistics” section). The study will be concluded, when all patients included have completed the study.

Handling of drugs

Storage

The active cream will consist of 25 mg/g melatonin as well as 150 mg/g DMSO, in a cream base. The placebo will consist of just the cream base. The cream base consists of polysorbate 80 (0,5%), cetostearyl alcohol (5%), paraffin oil (5%), glycerol monostearate 40-50 (6%), methyl

parahydroxybenzoate (0,1%), glycerol 85% (4%), sorbitol (7%), purified water (72,4%). The dose for each application will be 1 g, and the cream will be packaged in 30 g tubes. The tubes will be stored at room temperature, in a locked cabinet, in the office of one of the investigators. The cream will be produced and packaged by Glostrup Apotek in their manufacturing facility, according to EU GMP-guidelines. The tubes will be labelled with all required information listed in the EU GMP-guidelines concerning investigational medical products. All drugs will be delivered directly to the sponsor, who will document receiving the products according to GCP-guidelines (modtagekontrol).

Patients will be given one tube of cream at a time, and a second and third tube will be given to them, once the previous tube is empty or running low. Patients will be instructed to keep the tubes out of reach of children, away from sunlight and at room temperature. These instructions will also be listed on the label of the cream.

Administration

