The subjects will be questioned about adverse events once weekly during treatment. An adverse event is defined as any medical event that leads to an unwanted effect in the subject after the administration of the intervention medication, without any necessary connection between the adverse event and the intervention. An adverse reaction is defined as harm or unwanted reaction to a drug, no matter the dosage. We have defined six pre-specified self-reported symptoms (nervousness, confusion, depressed mood, dizziness, headache, or garlic like odor), based on the most commonly reported adverse reactions of melatonin and DMSO available in the literature [41, 50-53]. Patients will also be asked to report additional symptoms of adverse effects, if any. Both adverse reactions and adverse events will be reported in the eCRF.

Serious adverse events (SAE) are defined as any medical effect that result in death, are life-threatening, lead to hospitalization, result in disability or permanent damage, or any other important medical event. All serious adverse events will be registered in EudraCT..

Serious adverse drug reactions (SARs) will be reported annually. Most likely this will not be applicable to this study, as it will last less than a year. In this case, SARs will be reported on conclusion of the study.

Sudden unexpected serious adverse reactions (SUSARs) will be reported immediately to the Danish Medicines Authority and the local ethics committee. Adverse event registration will commence on the first study day and be finalized after the last study day. In case of serious adverse reactions, the sponsor can decide if the study will be terminated. It is the sponsor's responsibility to evaluate if an adverse event is a SUSAR. SUSARs that are lethal or life-threatening will be registered and reported to the Danish Medicines Agency as fast as possible and at the latest 7 days after the sponsor has obtained knowledge of such an adverse event. All other SUSARs will be reported to the Danish Medicines Agency within 15 days. Due to not expecting any serious adverse reactions, all SARs will be considered unexpected and therefore considered SUSARs.

Ethical considerations

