The study will be performed in accordance with the Helsinki II declaration. Patients will be included after oral and written consent. If patients do not wish to participate in the study, or choose to withdraw before administration of melatonin in any of the series of radiation therapy, they will receive standard treatment for their cancer. Patients can withdraw from the study at any time without stating a reason. Withdrawal from the study will not have any consequence for further treatment. Should an investigator deem it necessary for the safety of the patient, they can withdraw the patient from the trial. It is important to clarify if melatonin has a protective effect against

radiation injury, due to it having a large impact on the quality of life in patients. Positive results from this study will guide further studies and potentially change current practice in radiation oncology. The protective effect of melatonin has the potential to be used in several other types of cancer treatment, where ionizing radiation is used, to minimize the radiation injury and therefore decreased quality of life in patients. All information regarding participants in this study will be kept protected and no personal data will be published. The anonymity of all participants will be secured and data kept confidential.

Insurance

For this study no additional insurance policies have been arranged that exceed the *Danish Act on the Right to Complain and Receive Compensation within the Danish Health Service*

(Patientforsikringsloven). Patients participating in this study will be covered by the mentioned Act in accordance with “Bekendtgørelse af lov om klage- og erstatningsadgang inden for sundhedsvæsenet” in the same way as patients that are treated otherwise in the hospital. This is normal practice for investigator-initiated trials in Denmark.

Approvals

The study will be performed in accordance with the Helsinki II declaration. Approval from Danish Data Protection Agency in the Capital Region of Denmark (Datatilsynets fællesanmeldelse i Region H) will be sought in accordance with Data Protection Act (Databeskyttelsesloven), and the study will not start subject accrual before this approval has been given. The same applies for the local ethics committee as well as Danish Medicines Authority (Lægemiddelstyrelsen). Permission will be

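### The rule on stopping treatment contradicts the investigator's safety withdrawal, and the plan does not say whether outcome assessment continues once the cream is stopped

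*Combined protocol and SAP*

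**What the plan says.** **Stopping treatment.** Drop-outs and patient retention states: "Discontinuation of treatment will only occur in the following eventualities: the patient withdraws consent, or if the sponsor decides to terminate the study"; the sentence ends by tying termination to serious adverse events. The Adverse events section describes the same study-level power: "In case of serious adverse reactions, the sponsor can decide if the study will be terminated".

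**Withdrawal.** Ethical considerations says of the patient: "Patients can withdraw from the study at any time without stating a reason". Of the investigator it says: "Should an investigator deem it necessary for the safety of the patient, they can withdraw the patient from the trial".

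**Un-blinding.** Randomization and blinding allows an individual code break for safety: "Treatment allocation will only be un-blinded if it is imperative to the treatment of the patient". The allocation is then disclosed to one investigator other than the primary investigator. The section does not say whether the cream stops or assessments continue.

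**Data after drop-out.** Drop-outs and patient retention says: "All data from drop-outs will be used in statistical analyses". It also says: "If a patient does not wish to complete all three follow-up visits, some of the outcomes can be filled in electronically from home". The scope is then limited: "These outcomes are the QLQ-C30 and QLQ-BR23 questionnaires, and steroid usage outcomes".

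**Primary time points.** Statistical analyses places the RTOG score and image analysis two weeks after the last fraction, and QLQ-BR23 breast symptoms on the last day of radiation. It mentions missing data only in connection with the mixed linear model for the whole period.

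**The concern.** Two things are unclear. The first is whether an individual patient's treatment can be stopped for safety at all: one section's closed list leaves this out, and another section allows it.

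The second is what happens to outcome data afterwards. The only individual safety action in the text that would end treatment is withdrawal from the trial. A site could reasonably take that to mean no further visits. The patients concerned would then be missing at the primary time points for reasons that may relate to their skin or to tolerability of the cream. Only the active cream contains melatonin and DMSO (Handling of drugs, Storage), so loss could differ between arms. A comparison restricted to patients with a two-week value would then no longer be a comparison of the groups as randomised.

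**Working it through.** The contradiction is textual, and the plan gives no figure for it to reproduce. Arithmetic enters only in step 4.

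**1. Grounds for ending treatment**

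| Ground | Drop-outs and patient retention | Elsewhere |
|---|---|---|
| Patient withdraws consent | Listed | Ethical considerations agrees |
| Sponsor terminates the whole study | Listed | Adverse events agrees |
| Investigator withdraws one patient for safety | Not listed; excluded by the word *only* | Ethical considerations allows it |

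The third row cannot be reconciled as written. The un-blinding text does not settle it, and nothing says which section takes precedence.

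**2. What a safety withdrawal could cost, by primary outcome**

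Cream is used from the first to the last fraction, so a cream stop falls during radiation and before the two-week visit.

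- RTOG score, two weeks after the last fraction: needs a visit; not covered by home completion.
- Image analysis, two weeks after the last fraction: needs a photograph under controlled conditions; not covered by home completion.
- QLQ-BR23 breast symptoms, last day of radiation: at risk if withdrawal comes earlier. The home option is worded for the three follow-up visits, which come later.

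Using all data from drop-outs applies to values already collected. It does not create a two-week value.

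**3. What the analysis and recruitment rules do about it**

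Statistical analyses names t-tests or Mann-Whitney tests as examples of its group comparisons. It gives no missing-data rule for outcomes at a single time point. Sample size calculations continues inclusion until 48 patients have completed, and adds blocks if a group has fewer than 24. This restores the number of completers. It does not make them representative of everyone randomised.

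**4. Illustration of size (assumptions, not plan figures)**

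Inputs: 24 completers per group and the 41% melatonin incidence of grade 1-2 toxicity, both from Sample size calculations. Assumed: k = 1 to 4 melatonin patients withdrawn, none on placebo. Because inclusion continues until 24 complete, the k patients are additional to the 24.

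If all k would have had dermatitis, incidence among all randomised = (0.41 × 24 + k) / (24 + k), with 0.41 × 24 = 9.84:

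- k = 1: 10.84 / 25 = 43.4%
- k = 2: 11.84 / 26 = 45.5%
- k = 3: 12.84 / 27 = 47.6%
- k = 4: 13.84 / 28 = 49.4%

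The completers' 41% would be 2.4 to 8.4 points too favourable, against a planned difference of 90 − 41 = 49 points.

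If instead none of the k would have had dermatitis (for example, withdrawn for a symptom unrelated to it), incidence = 9.84 / (24 + k):

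- k = 1: 9.84 / 25 = 39.4%
- k = 4: 9.84 / 28 = 35.1%

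The completers' 41% would then be 1.6 to 5.9 points too unfavourable. The sign depends on who is withdrawn, which the documents do not tell us.

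**The case against.** The strongest reply is that no sentence says assessments cease after a safety decision. The protocol aims to promote retention and complete follow-up, keeps drop-outs' data and offers home completion. In a code break it keeps the allocation from the primary investigator, who assesses outcomes; this makes most sense if the patient may still be assessed. This stands. A reader might infer that the safety route necessarily removes the patient from follow-up, but the documents do not support that. They leave continued assessment unspecified, and that is the criticism.

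A reader might also infer that staff have no ground to stop cream for one patient's safety. That follows only from the closed list read alone; Ethical considerations supplies a ground. The defect is that the two sections disagree.

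A third tempting inference is that losses will probably be heavier on melatonin and will flatter it. The documents do not establish this. The section on DMSO reports mild, self-limiting burning with topical use at about 50 times the present dose, no serious reactions are expected, and the plan's own assumption puts skin toxicity at 90% on placebo against 41% on melatonin. Skin-related withdrawals could arise in either arm.

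Finally, the illustration concerns the incidence of grade 1-2 toxicity, whereas the primary analysis is of RTOG scores. That is correct, and it is why the figures are only illustrative. The protocol also promises a detailed analysis plan before study start. That could supply a missing-data rule, but it cannot recover visits that did not take place.

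**Conclusion.** The contradiction is certain: an exclusive list of two grounds sits beside a third ground in another section. It must be reconciled; which clinical rule prevails is for the sponsor.

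The statistical consequence is a risk, not a demonstrated loss. Because stopping cream is never distinguished from leaving the trial, a safety withdrawal may leave two of the three primary outcomes without a value, and the third as well if it comes before the last day of radiation. Neither the home option nor recruitment to 24 completers per group protects against the resulting selection.

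The size and direction of any bias are unknown. The 43% to 49% range rests on 1 to 4 additional withdrawals, all on melatonin, all with dermatitis and none on placebo. None of these assumptions comes from the documents, and changing the assumed dermatitis status reverses the sign. The point does not depend on that range. It is not fatal to the trial, but it should be corrected before the study starts.

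**What to change.** 1. Replace the conflicting text in Drop-outs and patient retention and in Ethical considerations with one statement of when treatment stops, and refer to it from the un-blinding paragraph. The content of that rule is the sponsor's clinical decision.
2. In that statement, define stopping the cream and withdrawing from the trial as separate events, each recorded with its date and reason.
3. State that whenever cream is stopped under the reconciled rule and the patient has not withdrawn consent to follow-up, the RTOG, photograph, questionnaire, steroid and adverse-event assessments in Table 3 continue as scheduled.
4. State that such patients are analysed in their allocated group. The promised analysis plan should say how missing values are handled for the three single-time-point primary outcomes.

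The cost is protocol wording and a small addition to the case report form. Table 3 already schedules the visits, and the sample size is unaffected.

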Melatonin has the disadvantage of being unstable when exposed to air and light. A study demonstrated that melatonin in aqueous solutions at room temperature, and at neutral pH, degrades by 29% over 21 days [26]. The compound dimethyl sulfoxide (DMSO) has seen wide use both as a solvent and as an anti-inflammatory drug [27, 28]. Based on a report made available to the authors from the pharmaceutical company, Bioneer A/S, melatonin dissolved in DMSO undergoes no degradation over 45 days when stored at 25 °C temperature, away from light.

The aim of the present randomized double-blinded placebo-controlled clinical trial is to investigate if melatonin can protect against acute radiation dermatitis in patients with early breast cancer receiving radiation therapy, and whether this has an impact on the patients' quality of life.

Study design

The study is registered at clinicaltrials.gov (indsæt ID, når dette er sket). This is protocol version 1.0, 13/09/2018. The study will be a randomized, placebo-controlled, double-blinded clinical pivotal trial. Patients will be allocated in a ratio of 1:1 to the melatonin or placebo group. Patients will be stratified according to the type of surgery (lumpectomy or mastectomy). Randomization will be performed in blocks of randomized sizes. The study will be performed in the Department of

Oncology, Rigshospitalet, Denmark. Patients will be included into our study according to specific eligibility criteria (see Table 1).

Interventions

Eligible patients with early breast cancer receive adjuvant radiation therapy over 15 to 30 daily fractions (5 fractions per week) of ionizing megavoltage photon radiation to a total of 40 - 60 Gy within 3-5 weeks according to the guidelines of the Danish Breast Cancer Cooperative Group [29].

In our study, the patients will administer approximately 1 g of cream containing melatonin (25 mg/g) and dimethyl sulfoxide (DMSO) (150 mg/g) or a placebo cream topically twice daily on the irradiated skin area. They are scheduled to do this every day from the first to the last fraction of radiation therapy, including the days where they do not receive radiation therapy. We have chosen placebo as our comparator due to it being safe, and in our view the most reasonable method of evaluating any effects of the intervention. On days where the patients receive radiation, the melatonin/DMSO or placebo cream will be applied no less than 2 hours prior to radiation.

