Prior to the first radiation treatment patients will receive a tube of cream with a number corresponding to their randomization number. They will be instructed in storage of the tube as described above. Patients will be seen once weekly throughout their radiation therapy. At this meeting, the patients will be asked how much cream they have left, and another tube of cream will be handed out when the patients are expected to run out of cream before the next meeting. Patients will receive a total of two to three tubes, depending on the number of radiation fractions they receive, each containing 30 g of cream.

Patients will be instructed to apply the cream twice daily, once in the morning and once in the evening. The patients will be instructed to apply approximately 1 g of cream in the treatment area twice daily. On days where the patients receive radiation fractions, the patients will be instructed to apply the morning dose no less than 2 hours prior to radiation. As part of the instruction, the investigator will weigh out 1 g of cream, so that the patient can see what amount of

cream they should apply each time. During the weekly visits, the patients will be asked if they are experiencing trouble applying the cream, and the investigator will help guide them. At every visit the patients will be asked to bring with them the tube of cream they are currently using. When first handed out, and during each visit, the tube will be weighed on a high-precision scale (range 0.01 mg to 200 g). Usage of cream will be calculated, usage will be evaluated. Furthermore, along with the first tube of cream, the patients will receive a schedule with the relevant dates for the patient; the patient will have to fill in every time they have applied the cream. When a patient is expected to run out of cream before the next visit, another tube will be handed to them. One tube of cream contains 30 g of cream, and the patients will apply 2 g each day they receive radiation. One tube should last for 15 days, assuming they administer the correct dose daily, and assuming they are able to completely empty the tube. Ideally patients will receive new tubs on Study visit week 2 and 4, if they have managed to use the instructed dose.

Statistics

Sample size calculations

In order to establish the needed number of patients for the study, we have performed 3 separate sample size calculations.

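### The active cream adds both melatonin and DMSO to the base, so the trial can test the combined cream but not melatonin, which is what the aim names

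*Combined protocol and SAP*

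**What the plan says.** The introductory text before Study design states the aim as "to investigate if melatonin can protect against acute radiation dermatitis in patients with early breast cancer" and asks whether this affects quality of life. Study design names the groups in the same way: "Patients will be allocated in a ratio of 1:1 to the melatonin or placebo group".

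The product is described differently. Under Interventions, patients apply "cream containing melatonin (25 mg/g) and dimethyl sulfoxide (DMSO) (150 mg/g) or a placebo cream topically twice daily". Storage repeats the two concentrations and adds "The placebo will consist of just the cream base". Randomization and blinding uses a combined label: "Every assignment will contain a code that corresponds to tubes of the melatonin/DMSO or placebo preparation". Interventions also uses the combined label in its sentence on application before radiation. It justifies the placebo as "in our view the most reasonable method of evaluating any effects of the intervention", without mentioning DMSO.

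On DMSO, the introductory text says: "The compound dimethyl sulfoxide (DMSO) has seen wide use both as a solvent and as an anti-inflammatory drug". The section on adverse reactions to DMSO adds that it is used on its own to treat interstitial cystitis, and that topical use has caused mild burning at roughly 50 times the local dose planned here.

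Ethical considerations presents the trial as clarifying whether melatonin protects, extends the expected benefit of melatonin to other cancers, and says positive results could alter radiotherapy practice.

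**The concern.** The question asked and the contrast made are not the same. A placebo that isolates melatonin would contain everything in the active cream except melatonin; this one also leaves out DMSO. The three primary outcomes are the RTOG skin grade, photographic erythema and self-reported breast symptoms, and an anti-inflammatory agent on the skin could plausibly move all of them. Nothing in the text states or defends an assumption that DMSO has no effect on them.

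The direction is open. An anti-inflammatory action would make melatonin look better than it is; local irritation would hide part of its benefit. The components may also interact: the erythema sample size assumes that the melatonin is fully dissolved, and DMSO is introduced as a solvent.

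The trial is called pivotal and is meant to guide later studies and practice. If a positive result is read as the aim is worded, it will be credited to melatonin on data that support only the combined product.

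**Working it through.** **1. What differs between the creams** (Handling of drugs, Storage)

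- Base ingredients: 0.5 + 5 + 5 + 6 + 0.1 + 4 + 7 + 72.4 = 100.0%. DMSO is not listed and there is no remainder for it.
- Active minus placebo: 25 + 150 = 175 mg/g, of which DMSO is 150/175 = 86% by mass.
- Per day, at two applications of 1 g: 2 × 25 = 50 mg melatonin and 2 × 150 = 300 mg DMSO, against 0 and 0.

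These are composition figures. A mass share is not a share of the effect.

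**2. What the contrast identifies**

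Let M and D indicate the presence of melatonin and DMSO, with mean outcome = b0 + bM·M + bD·D + bMD·M·D. The design has only the cells (M, D) = (0, 0) and (1, 1). Their rows in the design matrix are (1, 0, 0, 0) and (1, 1, 1, 1), so its rank is 2. The difference between arms is bM + bD + bMD: one equation in three unknowns. More patients estimate the sum more precisely but never split it.

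**3. Whether actual use could separate the components**

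Administration provides a measure of exposure: "When first handed out, and during each visit, the tube will be weighed on a high-precision scale". For w grams used, melatonin is 25w mg and DMSO is 150w mg, so DMSO is six times melatonin in every patient on active cream. The two exposures are perfectly collinear, and a dose-response analysis does not help.

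**4. Illustration on the plan's own breast-symptom figures**

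Inputs from Sample size calculations: mean 82.2, target 70 (difference 12.2), SD 15.1, alpha 5%, power 80%. The plan does not state sidedness; two-sided is assumed. With the normal approximation:

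- n per arm = 2 × (1.960 + 0.842)² × 15.1² / 12.2² = 24.05. The plan has 24; strict rounding up gives 25.
- Power at 24 per arm = Φ(12.2 / (15.1 × √(2/24)) − 1.96) = Φ(0.839) = 79.9%.

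The plan's figure is reproduced to within one patient per arm. Now assume additive effects, with a share s of the 12.2 points due to DMSO. The documents give no value for s, so the range 0 to 1 is shown.

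| s | Melatonin-only difference | Power, active vs base (as planned) | Power at 24 per arm, active vs a control containing DMSO |
|---|---|---|---|
| 0 | 12.2 | 79.9% | 79.9% |
| 0.25 | 9.15 | 79.9% | 55.5% |
| 0.5 | 6.1 | 79.9% | 28.8% |
| 0.75 | 3.05 | 79.9% | 10.4% |
| 1 | 0 | 79.9% | no true effect |

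The third column does not change: the planned comparison is as likely to be positive when melatonin does nothing as when it does everything. The table covers only a helpful DMSO effect. A harmful one would work the other way.

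**The case against.** The strongest reply is that the trial compares products and does so validly. Both concentrations are stated, the combined label already appears in Interventions and in Randomization and blinding, DMSO has its own harms section, and the placebo is justified by reference to the intervention as a whole. On this reading, melatonin is shorthand, the sentences in Ethical considerations are outlook and not a rule for conclusions, and neither the statistics section nor the publication plan commits to a melatonin-specific claim.

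The evidence that DMSO acts here is also thin. The text introduces it mainly to keep melatonin stable, its use on its own is for a bladder condition, and the burning occurred at a far higher local dose. No section reports an effect of DMSO at 150 mg/g on any primary outcome.

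Much of this stands. The randomised comparison is sound, the composition is disclosed, and a material DMSO effect is possible but not shown. It does not rescue the aim, which is the trial's formal question and names melatonin alone, as do the group names. Mixed labels are a reason to reconcile the text. If DMSO is only the vehicle, a vehicle control would contain it. And lack of evidence of an effect on these outcomes does not support an unstated assumption of none, when the same document calls DMSO an anti-inflammatory drug.

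**Conclusion.** The concern holds. As written, the plan sets an aim that its two arms cannot answer at any sample size. The arms identify the effect of the melatonin/DMSO cream against cream base, and nothing finer.

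The defect is one of attribution. The tests, error rates, product-level estimate and 48 evaluable patients are not affected. The size and direction of any DMSO contribution are unknown, and no bias figure is claimed; the table above is an illustration under additivity and an assumed share. The conclusion rests on the stated composition and on the absence, in the text available, of any statement that DMSO is inert on these outcomes or that conclusions are limited to the combined cream. The detailed analysis plan promised under Statistical analyses is not among the documents and could still carry that limit.

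**What to change.** Reconcile the wording before the study starts:

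- **Aim:** *to investigate whether a cream containing melatonin and DMSO, compared with its cream base, reduces acute radiation dermatitis*, with the rest of the sentence unchanged.
- **Study design, arm names:** *melatonin/DMSO cream or cream-base placebo*, used throughout.
- **Storage, and the detailed analysis plan:** *The active and placebo creams differ in both melatonin and DMSO. The trial does not separate the two, and no effect specific to melatonin will be claimed.*
- **Ethical considerations:** name the melatonin/DMSO cream in the two sentences on protective effect and, for consistency, in the sentence on withdrawal before treatment.

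The cost is these edits and the loss of the melatonin-specific claim. Product, sample size, tests and visits stay as they are. To keep that claim, the comparator would have to contain every ingredient of the active cream except melatonin. That is a larger product change and the sponsor's decision.

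A separate, optional precaution concerns blinding. The primary investigator collects all outcomes, and a garlic-like odour is a listed DMSO reaction and a pre-specified symptom. Grading the skin and taking the photographs before asking about adverse events adds no visit. It would not remove impressions from earlier visits, hide an odour noticed in person or protect the self-reported questionnaire, and the documents do not give the odour's frequency at this dose.
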